#### Randomized, Double-Blind, Placebo-Controlled Part:

A total of 2000 subjects will be randomized to receive Aramchol or matching placebo employing a permuted blocks of 2:1 randomization scheme, respectively.

The Randomized, Double-Blind, Placebo-Controlled Part consists of 2 phases; an initial phase with a Histology-Based endpoint, and a subsequent Phase with a Clinically-Based endpoint. Throughout the duration of both study phases, subjects will be treated with either Aramchol or matching placebo according to the randomization scheme generated prior to study initiation.

In order to preserve the integrity of the Randomized, Double-Blind, Placebo-Controlled Part the following will be performed:

 Subjects, sites and Sponsor personnel will be kept blinded to treatment assignment until EoS.

Both study Parts (Open-Label Part and Randomized, Double Blind, Placebo-Controlled Part) will be closely monitored by an unblinded independent Data Monitoring Committee (DMC) according to a pre-defined DMC charter. The DMC will meet periodically (at least every 3-4 months) assess the ongoing accumulated study data to ensure study subject welfare.

[figure not shown]
Clinical outcome events, possible DILI and major adverse cardiovascular events (MACE) will be adjudicated by the following independent adjudication committees for both study Parts (Open-Label Part and Randomized, Double Blind, Placebo-Controlled Part):

- Clinical Outcome Adjudication Committee (COAC) will adjudicate predefined clinical outcome events (all-cause mortality, liver transplant, progression to cirrhosis, change in MELD score to > 15 and hospitalization due to hepatic decompensation events).
- Cardiac Adjudication Committee (CAC) will adjudicate Major Adverse Cardiovascular Events (cardiovascular death non-fatal myocardial infarction, non-fatal stroke), hospitalization for unstable angina or heart failure, and all-cause mortality.
- Hepatic Safety Adjudication Committee (HSAC) will adjudicate hepatic safety events including cases of suspected DILI as well as non-endpoint hepatic/hepatobiliary SAEs.

[figure not shown]

Duration	
Duration	Open-Label Part:
	Screening: up to 8 weeks
	Treatment period: The Open-Label Part will continue for the same duration as the Randomized, Double-Blind, Placebo-Controlled Part. All subjects in the Open-Label Part will receive Aramchol 300mg BID until End of study (EoS).
	Randomized, Double-Blind, Placebo-Controlled Part:
	Screening: up to 8 weeks

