#### Randomized, Double-Blind, Placebo-Controlled Part:

Screening: up to 8 weeks.

Treatment period: Subjects will remain on the same treatment assignment for up to 7 years.

**End-of-Study**: All 2000 subjects planned to be randomized into this study will receive Aramchol or matching placebo until EoS which will occur at the time when a total of 380 subjects will experience at least 1 pre-specified clinical event or at 5 years from last subject's randomization, whichever comes first.

Both study parts (Open Label Part and Randomized, Double Blind, Placebo Controlled Part):

**Study Visits:** All subjects will attend the following visits: Screening, Baseline, weeks 4, 8, 12, and every 12 weeks thereafter.

[figure not shown]
Visit scheduling for subjects who switch from the Randomized, Double-Blind, Placebo-Controlled Part to the Open-Label Part is dependent on prior exposure to Aramchol. Subjects that received active treatment will continue based on scheduled visits. Subjects that received placebo will start the scheduled visits from a Baseline visit

At the visit when the switch is performed, subjects will sign a new ICF and complete activities as applicable (e.g. laboratory, imaging, stool samples).

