# 8.2.5 Randomized, Double-Blind, Placebo-Controlled Part Scheduled visits (not including End of Study visit)

Following the Baseline visit, the following assessments will be performed during scheduled visits at Week 4, 8, 12, and every 12 weeks thereafter.

The following should be performed/assessed during the visit:

- Physical examination at weeks 24 and every 24 weeks thereafter
- Body measurements including weight and waist circumference at week 12 and every visit thereafter
- Vital signs including blood pressure, heart rate, respiratory rate, and temperature
- Dietary and lifestyle changes as well as change in physical activity regimen will be assessed, and subjects will be counseled
- Concomitant medications
- Adverse Events
- ECG
- Laboratory:

Fasting (8 hours) is required before the visit

- A urine pregnancy test in women of childbearing potential
- Complete blood count and serum biochemistry will be measured at every study visit
- o Renal function (creatinine and eGFR) will be measured at every study visit
- Coagulation at every visit
- CPK will be measured at weeks 24 and every 24 weeks thereafter
- Glycemic parameters: fasting glucose will be measured at every study visit. HbA1c,
   C-peptide, Insulin and HOMA-IR at weeks 12,24 and every 24 weeks thereafter
- Thyroid function (TSH, T3 and T4) will be measured at week 48
- MELD will be calculated at week 12, and at every visit thereafter
- Blood sample for PK will be collected from week 4 until 72 weeks and every 24 weeks thereafter
- Blood samples for potential biomarkers (including ProC3 and ELF), metabolomics and better understanding of mechanism of action will be collected at week 12 24, 48 and every 24 weeks thereafter
- Drug accountability
- Study drug dispensing
- Abdominal ultrasound (US) and Fibroscan will be performed at week 24 and every 24
  weeks thereafter
  - Abdominal US is performed to assess for signs of HCC or other RUQ new findings as well as signs of progression to cirrhosis (e.g. ascites, splenomegaly)

- Fibroscan is performed as part of the NITs assessment in the study. Scan should meet the minimal quality definition (subject fasting for a minimum of 3 hours and at least 10 valid shots with IQR≤30% of the value of the median)

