## Randomized, Double-Blind, Placebo-Controlled Part:

Aramchol 300mg BID or matching placebo will be administered in a blinded manner. To maintain the blind, Aramchol and matching placebo capsules will have identical appearance and will be packaged in identical bottles.

Participating subjects, Investigators, the Sponsor and any personnel involved in subjects' assessments, monitoring, analysis and Data Management will be kept blinded to the treatment assignment, excluding the designated personnel in clinical supply vendor and the RTSM vendor.

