#### 9.7 Pharmacokinetics

Blood sample for analysis of concentrations of Aramchol and its metabolites as well as for population PK will be collected at all study visits from week 4 until week 72 and every 24 weeks thereafter and at early termination/study completion. Subjects attending a site visit in the morning should take their dose as usual in the evening before the visit and should record the time of dosing. They should NOT take their dose on the morning of their visit until after the blood sample for PK has been drawn. Subjects attending a site visit in the afternoon should take their morning dose as usual and should record the time of dosing.

The Investigator will record the timing the subject has taken the last tablet prior to blood drawing and the time of PK sampling.

Samples will be used for pharmacokinetic endpoints analysis and safety if deemed necessary.

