If data are processed from other than subject clinical sources (e.g. central laboratory, bioanalytical laboratory, central reading center), the results will be sent to the study site, in a secure and encrypted manner, where they will be retained and might be transcribed to the CRF, if applicable. These data sets may also be sent electronically to the Sponsor (and/or organization performing Data Management) as part of the clinical database. All data from other sources will be available to the Investigator(s).

For subjects who sign the ICF and perform screening procedures but do not enroll in the study, for any reason, the required data will be entered into the CRF, according to the instructions detailed in the eCRF completion guidelines.

Any processing of Subject's Data shall be solely to the extent required and subject to the informed consent provided, for the purpose of complying with data minimization principles. No additional data shall be processed without applicable informed consent. Further, Subject Data shall be used or shared solely for the purpose of the study, as set forth herein or otherwise instructed by the Sponsor in writing and consented by the subject. Using Subject's Data for any other purposes is strictly forbidden.

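### Section 12.6.1 sends bioanalytical results to sites with no exemption for Aramchol concentrations in the double-blind part, which contradicts the plan's own blinding commitments

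*Combined protocol and SAP*

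**What the plan says.** **Blinding commitments.** The Synopsis (Study Design, double-blind part) states: "Subjects, sites and Sponsor personnel will be kept blinded to treatment assignment until EoS". Section 8.4.3 says that subjects, investigators, the Sponsor and those doing assessment, monitoring, analysis and data management "will be kept blinded to the treatment assignment, excluding the designated personnel in clinical supply vendor and the RTSM vendor". Later paragraphs of 8.4.3 add an independent unblinded statistician who prepares DMC reports, dedicated staff for SUSAR reporting, and a firewalled taskforce for the week-72 analysis. They also state that individual assignments and listings go only to that taskforce and to regulators. The bioanalytical laboratory and concentration data are not mentioned.

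**Concentration data.** Section 9.7: "Blood sample for analysis of concentrations of Aramchol and its metabolites as well as for population PK will be collected at all study visits", starting at week 4. Section 8.2.5 confirms this for the double-blind part: "Blood sample for PK will be collected from week 4 until 72 weeks", then every 24 weeks. Section 7.5.2.1.1 adds an Aramchol sample when suspected DILI is being confirmed. Section 9.7 also allows the samples to be used for safety if that is judged necessary.

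**Routing of results.** Section 12.6.1, on data from other than subject clinical sources: "e.g. central laboratory, bioanalytical laboratory, central reading center), the results will be sent to the study site". It continues that the data sets may also go to the Sponsor or the organisation performing data management, and ends: "All data from other sources will be available to the Investigator(s"). No exemption for concentrations and no timing is given.

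**Switchers.** Section 8.1, on subjects who move to the Open-Label Part: "Subjects that received active treatment will continue based on scheduled visits. Subjects that received placebo will start the scheduled visits from a Baseline visit".

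**The concern.** In a trial of one drug against placebo, a plasma concentration of that drug is close to a treatment code. Section 12.6.1 names the laboratory that produces it, directs its results to the site and gives investigators access. A site that follows 12.6.1 therefore cannot also satisfy 8.4.3.

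The blind matters here because several steps rest on judgement at the site. These include the suspicion-triggered liver biopsy, which is recommended but not mandatory (8.2.5), the recommended biopsy after treatment discontinuation (8.2.8), stopping treatment, AE causality, and keeping the subject in the study for the week-72 and 5-year biopsies. Histological progression to cirrhosis is a component of the clinical primary endpoint, so uneven triggering of biopsies could affect it. Uneven dropout could affect the histology endpoint.

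The plan itself treats individual unblinding as serious: a subject unblinded in an emergency is withdrawn, and the Sponsor stays blind even to SUSAR assignments (8.4.3, 8.4.4).

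**Working it through.** The plan states no figure on this point, so there is none to reproduce. The check is a side-by-side reading with simple counts.

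1. **Does the assay identify the arm?** Section 3.2 describes Aramchol as a synthetic conjugate, and Section 7.2 disallows other investigational products. A quantifiable level therefore points to the Aramchol arm. Repeated absence points to placebo, or to non-adherence or stopped treatment. The assay limit is not given; I assume that it detects drug in an adherent subject. Hence the concentrations largely, not perfectly, identify the arm.

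2. **How many samples?** Visits fall at weeks 4, 8 and 12 and every 12 weeks after (8.1). Up to week 72: 3 + (72 − 12)/12 = 3 + 5 = 8 samples (weeks 4, 8, 12, 24, 36, 48, 60, 72). Then every 24 weeks, from week 96 to week 240: (240 − 96)/24 + 1 = 7 more before 5 years. Any DILI work-up sample is extra.

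3. **How many subjects could be reached?** With 2:1 allocation, 2000 × 2/3 ≈ 1333 Aramchol and 2000 × 1/3 ≈ 667 placebo. In the first 1000, used for the histology endpoint: about 667 and 333.

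4. **Do the passages conflict?**
   - Sites: blinded until end of study (Synopsis), but 12.6.1 says that bioanalytical results will be sent to them.
   - Investigators: blinded (8.4.3), but with access to all external data (12.6.1).
   - Data management: "analysis and Data Management will be kept blinded to the treatment assignment" (8.4.3), but a permitted recipient (12.6.1).
   - Sponsor: blinded (Synopsis, 8.4.3), but a permitted recipient (12.6.1, optional).
   - Individual listings: taskforce and regulators only (8.4.3), but 12.6.1 opens a wider route.

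   In 12.6.1 the qualifier about applicability attaches to transcription into the CRF, not to transfer or access. The conflict is therefore in the text.

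5. **Switch rule.** Continuing the schedule or restarting it at Baseline depends on the former arm, so carrying out the rule reveals that arm. The Open-Label Part has 150 subjects in total, so switchers number at most 150/2000 = 7.5% of the double-blind target. The actual number is not given.

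6. **Spill-over from switchers to subjects who stay blinded.** Block size is not shown, so I assume 3, 6 or 9. If one placebo subject in a 2:1 block is known, the chance that another subject in that block is on Aramchol rises from 2/3 (67%) to 2/2 = 100%, 4/5 = 80% or 6/8 = 75%. This applies only if block membership can be inferred. Blocks are stratified by country or region and fibrosis stage, not by site (8.4.2), so the documents do not show that a site could do so.

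**The case against.** The best defence is that 12.6.1 is a general data-handling clause. It lists the bioanalytical laboratory as an example, does not mention Aramchol concentrations, gives no timing, and covers the Open-Label Part, where there is nothing to blind. Transfer to the Sponsor is optional. The specific rules in the Synopsis and 8.4.3 are explicit, and a reader could let them prevail. Section 10 already gives concentration data an unblinded route: the DMC may review pharmacokinetic data, in reports from an independent unblinded statistician. Parts of the protocol are not visible, and a laboratory or data management plan may hold a firewall.

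Most of this stands, and it limits the finding. A reader might infer that the blind has failed, or that all 2000 subjects will be unblinded. The documents do not support that: they show a rule that would unblind if followed literally, not that results are released before end of study. But the defence does not remove the contradiction. The clause names the laboratory, says that results will be sent, and no visible text withholds them.

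A reader might also infer that the switch rule biases both primary endpoints. That is not shown. It discloses the former arm only of subjects who have left for open-label drug, and the Synopsis rationale and Section 3.4.1 exclude Open-Label histology and clinical events from both primary endpoints. Blinded central reading and adjudication (8.4.3) also limit bias by either route, though they do not protect site decisions on whether a biopsy is taken.

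**Conclusion.** The point holds as a contradiction in the current text that needs correcting. Section 12.6.1 as written routes arm-identifying concentrations to sites and investigators and permits their transfer to the Sponsor and data management, against the commitments in the Synopsis and 8.4.3. The reach, if the clause is followed, is any sampled double-blind subject, with 8 scheduled samples before the histology endpoint. No size of bias can be derived from the documents, and none is claimed.

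This rests on two assumptions: that the assay separates the arms in adherent subjects, and that no firewall exists in text that was not available.

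The switch rule is secondary. It conflicts with the unqualified promise in the Synopsis for at most 150 subjects (7.5% of 2000). It calls for reconciliation, not for a claim of bias in the primary comparisons.

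**What to change.** 1. **Section 12.6.1:** exempt Aramchol and metabolite concentrations of the double-blind part, including the DILI work-up sample in 7.5.2.1.1, from release to sites, the blinded Sponsor team and data management until end-of-study unblinding.
2. **Access before then:** allow it only to the bioanalytical laboratory, firewalled pharmacokinetic staff, the independent unblinded statistician and DMC (consistent with Section 10), and the firewalled taskforce.
3. **Section 8.4.3:** list these parties as exceptions to the blind.
4. **Section 9.7:** reconcile the stated safety use of samples with the blind, so that the text says who would see such a result.
5. **Section 8.1 against the Synopsis:** state who learns a switcher's former arm, and when.

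Item 5 should not be solved by restarting every switcher on one schedule. The Open-Label primary endpoint is histology after 24, 48 or 72 weeks of treatment (4.1.1). A restart would place the biopsies of subjects with prior Aramchol after longer exposure than their nominal week. Deriving exposure at analysis cannot move a biopsy already taken.

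The cost is protocol and data-transfer wording. The small downside is that concentration data enter the main database only after unblinding.

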#### 12.6.2 Study Discontinuation and Closure

All 2000 subjects planned to be randomized into the Randomized Double-Blind, Placebo-Controlled Part will receive Aramchol or matching placebo until EoS which will be announced at the time when a total of 380 subjects will experience at least 1 pre-specified clinical event or at 5 years from last subject randomization, whichever comes first.

The Open-Label Part will continue for the same duration as the Randomized, Double-Blind, Placebo-Controlled Part.

All subjects in the Open-Label Part will receive Aramchol 300mg BID until End of study (EoS). Premature termination or suspension of this study may occur due to regulatory authority decision, IEC/IRB opinion, drug safety reasons, and DMC recommendation or at the discretion of the Sponsor. The Sponsor retains the rights to discontinue the development of the investigational product at any time.

If the study is prematurely terminated, the Sponsor will promptly notify the Investigators and the relevant regulatory authorities as required. The Investigator should promptly notify the IEC/IRB and the study participants and assure appropriate therapy and follow-up.

#### 12.6.2.1 Declaration of the End of the Clinical Trial

For clinical investigational centers, EoS declarations will be in accordance with local regulations.

## 12.6.3 Study Records Retention

The Investigator or institution shall retain all essential study documentation and records generated before, during, and after the study ("Study Records"). The Study Records should be kept at the clinical site or a designated, secured, off-site storage facility with limited access.

The Sponsor specific essential documents and The Study Records should be retained until at least 2 years after the last approval of a marketing application in an ICH region and until there are no pending or contemplated marketing applications in an ICH region or at least 2 years have elapsed since the formal discontinuation of clinical development of the investigational product. These documents should be retained for a longer period however if required by the applicable regulatory requirement(s) or if needed by the Sponsor.

If the Investigator becomes unable to continue to retain Study Records for the required period, the Sponsor should be prospectively notified, and the study records must be transferred to a designee as agreed by the Sponsor.

## 12.7 Future Use of Stored Specimens and Data

The Study Records, aggregated data and statistics as well as certain study subjects' personal information and biospecimens (such as blood samples or tissue biopsies) collected during the study may be stored and used for future research. Personal information and samples from this study that will be used for future research may be coded (include the study subject code) or de-identified. If any future research requires use of de-identified or anonymized personal information or samples, all personal identifiers will be removed from them, including the study code, so that the information or samples will be considered to be de-identified or anonymized as defined under applicable Data Protection Laws and cannot be linked back to the subject.

If required by law, the Investigator shall ensure the subject consents to future use of their samples and information through the ICF

The aforesaid coded, de-identified or anonymized samples and information may also be shared with third parties with whom the Sponsor collaborates even if it exceeds the scope of the clinical trial.

## 12.8 Reporting and Publication of Results

The Sponsor is responsible for ensuring that the public has access to the appropriate information about the study by conforming to local and regional requirements for registration in clinical trial registries and posting of results. This study will be registered on clinical trials registry websites according to standard procedures.

The Sponsor is responsible for preparing a clinical study report, in cooperation with the Principal Investigator.

No data that result from the study and none any of the information provided by the Sponsor to the Investigators for the purpose of conducting the study, will be published or passed on to any third party, without prior written consent of the Sponsor. Policies regarding the publication of the study results are defined in the Clinical Trial Agreement.

No patent application(s) based on the results of the study may be made by the Investigator or Institution nor may assistance be given to any third party to make such an application without the written authorization of the Sponsor.

### 12.9 Liability and Insurance

This clinical study is insured in accordance with the corresponding local legal provisions.

The policy coverage is subject to the full policy terms, conditions, extensions, and exclusions.

Excluded from the insurance cover are, inter alia, damages to health and worsening of previous existing disease that would have occurred or continued if the subject had not taken part in the clinical study.

The policy of Clinical Trials Insurance will be provided to the investigational centers by the Sponsor where required.

**ARMOR Study** 

### 12.10 Vendors

Certain study activities will be performed by Sponsor-designated vendors. These may include, among others, a contract research organization, a central laboratory, biopsy reading center, clinical supply management, and data management. The list of vendors is available in the trial master file and will be updated as necessary.

